## **7.2 Baseline visit (week 0)**

The following tasks will be conducted at this visit:

- Assessment of concomitant medications.
- Complete physical examination, vital signs, and weight.
- Laboratory studies: urine pregnancy test in women of childbearing potential, hsCRP, serum chemistries, complete blood count with automatic differential, lipid panel, and stool calprotectin.
- Calculation of CDAI and PRO2 scores
- Eligibility assessment based on collected data.
- Study therapy dispensed and instructions on use given.
- Adverse event monitoring.
- Review of bowel movement diary.
- IBDQ and SF-36 assessments.
- Randomization of subjects to treatment arm via REDCap by research pharmacist. (Both subject and clinical staff will be masked to treatment group assigned.)

## **7.3 Weeks 2, 4, 6, 8, and 10 ( $\pm 3$ days)**

These visits may be conducted within three days of the specific time-point marking the number of weeks since baseline visit. The following tasks will be conducted at these visits:

- Assessment of concomitant medications.
- Targeted physical examination (eyes, throat, lymph nodes, cardiopulmonary systems, abdomen, musculoskeletal, extremities, and skin), vital signs, and weight.

- Laboratory studies: urine pregnancy test in women of childbearing potential, serum posaconazole concentration, hsCRP, serum chemistries, lipid panel, complete blood count with automatic differential, and stool calprotectin.
- Study therapy usage reviewed, and further study drug dispensed
- Adverse event monitoring.
- Review of bowel movement diary.
- Calculation of CDAI and PRO2 scores
- IBDQ and SF-36 assessments.
- Stool collection for microbiome analysis

#### **7.4 Week 12 ( $\pm 3$ days) or early termination**

This visit may be conducted within three days of the specific time-point marking the number of weeks since baseline visit. The following tasks will be conducted at these visits:

- Assessment of concomitant medications.
- Complete physical examination, vital signs, and weight.
- Laboratory studies: urine pregnancy test in women of childbearing potential, serum posaconazole concentration, hsCRP, serum chemistries, complete blood count with automatic differential, lipid panel, and stool calprotectin, microbiome, blood for transcriptomics.
- 12-lead EKG.
- Study therapy usage reviewed.
- Adverse event monitoring.
- Review of bowel movement diary.
- Calculation of CDAI and PRO2 scores
- IBDQ and SF-36 assessments.
- Colonoscopy with biopsies (RNALater & Formalin) and washings scheduled  $\pm 7$  days of this visit for calculation of SES-CD. Biopsies and washings should be obtained from same area of each region as screening samples.
- Following the above evaluations, subjects will be unblinded and determined to have received either posaconazole or placebo during the 12-week induction period.
- Patients meeting criteria for active disease AND who are determined to have received placebo will be eligible to receive open label posaconazole; these subjects will be dispensed 4 weeks posaconazole at this visit.

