**Absorption**

When given orally in healthy volunteers, posaconazole delayed-release tablets are absorbed with a median Tmax of 4 to 5 hours. Steady-state plasma concentrations are attained by Day 6 at the 300 mg dose (QD after BID loading dose at Day 1). The absolute bioavailability of the oral delayed-release tablet is approximately 54% under fasted conditions. The Cmax and AUC of posaconazole following administration of posaconazole delayed-release tablets is increased 16% and 51%, respectively, when given with a high fat meal compared to a fasted state (see Table 1). In order to enhance the oral absorption of posaconazole and optimize plasma concentrations, posaconazole delayed-release tablets should be administered with food. Concomitant administration of posaconazole delayed-release tablets with drugs affecting gastric pH (Mylanta®, ranitidine (Zantac®), esomeprazole (Nexium®)) or gastric motility (metoclopramide (Reglan®)) did not demonstrate any significant effects on posaconazole pharmacokinetic exposure (posaconazole, package insert).

**Table: Statistical Comparison of Plasma Pharmacokinetics of Posaconazole Following Single Oral Dose Administration of 300 mg Posaconazole Delayed-Release Tablet to Healthy Subjects under Fasting and Fed Conditions**

| Pharmacokinetic Parameter              | Fasting Conditions |                      | Fed Conditions (High Fat Meal)* |                       | Fed/Fasting       |
|--|--------------------|----------------------|---------------------------------|-----------------------|-------------------|
|  | N                  | Mean (%CV)           | N                               | Mean (%CV)            | GMR (90% CI)      |
| Cmax (ng/mL)         | 14                 | 935 (34)             | 16                              | 1060 (25)             | 1.16 (0.96, 1.41) |
| AUC0-72hr (hr·ng/mL) | 14                 | 26200 (28)           | 16                              | 38400 (18)            | 1.51 (1.33, 1.72) |
| Tmax† (hr)           | 14                 | 5.00
(3.00, 8.00) | 16                              | 6.00
(5.00, 24.00) | N/A               |

GMR=Geometric least-squares mean ratio; CI=Confidence interval

\* 48.5 g fat

† Median (Min, Max) reported for Tmax

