### **5.7 Open Label Posaconazole:**

At 12 weeks, subjects will undergo colonoscopy and clinical assessment for response, after which they will be unblinded. Subjects who meet criteria for active disease AND who are determined to have received placebo will be eligible to receive 12 weeks of open-label posaconazole. Eligibility Criteria for open label posaconazole:

1. Endoscopically-confirmed active Crohn's disease with active disease defined by SES-CD  $\geq 6$  ( $\geq 4$  if ileal only) based on local reading, AND
2. Active symptoms of Crohn's disease (CDAI  $>220$ ), AND
3. Received placebo during the 12-week induction period

Subjects who meet the above criteria and opt to receive open label posaconazole will be monitored for safety / adverse events at follow-up visits. Changes in corticosteroid dosing will be permitted after 12 weeks, regardless of whether subjects are receiving posaconazole or not. All subjects will undergo colonoscopy at 36 weeks.

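### The Week 12 colonoscopy may fall up to 7 days after the visit at which open-label drug is dispensed; the rules then conflict, and keeping the stated order can put the primary endpoint off drug

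*Combined protocol and SAP*

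**What the plan says.** Section 7.4 sets two nested windows. For the visit: "This visit may be conducted within three days of the specific time-point marking the number of weeks since baseline visit". The colonoscopy, with biopsies and washings, is then scheduled within plus or minus 7 "days of this visit for calculation of SES-CD". Table 1 lists the same colonoscopy under a Week 12 column with a window of plus or minus 3 days.

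On order, Section 7.4 says: "Following the above evaluations, subjects will be unblinded and determined to have received either posaconazole or placebo during the 12-week induction period". The colonoscopy is the last item listed above that line. Section 5.7 agrees: "At 12 weeks, subjects will undergo colonoscopy and clinical assessment for response, after which they will be unblinded".

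On open-label entry, Section 5.7 requires "Endoscopically-confirmed active Crohn's disease with active disease defined by SES-CD" of at least 6 (at least 4 if ileal only) "based on local reading, AND" a CDAI above 220, together with assignment to placebo. For subjects who qualify, Section 7.4 says that "these subjects will be dispensed 4 weeks posaconazole at this visit". Section 6.7.3 and Table 1 also put the first open-label dispensing at Week 12.

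On blinded supply, Section 6.7.3 dispenses two-week supplies from baseline to Week 10, and Section 6.2 sets therapy at 12 weeks. No blinded supply is listed for Week 12.

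**The concern.** SES-CD response at Week 12 is the sole primary endpoint (Section 4.2). Malassezia in the Week 12 washings is a key secondary endpoint (Section 4.3). Both come from this one colonoscopy.

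If the colonoscopy follows the visit, the SES-CD that decides open-label entry does not yet exist on the day the drug is to be dispensed. The site must choose between two courses:

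- **It keeps the stated order and waits.** The endpoint is then measured after the visit, when the planned blinded supply may have run out. Loss of drug can change only the posaconazole arm. CDAI and PRO2, taken at the visit, may also describe a different treatment state from the SES-CD.
- **It takes the same-visit instructions literally.** It then departs from the stated order and risks unblinding before the endpoint is measured.

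The plan does not say which course applies.

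**Working it through.** **1. The plan's own figure.** Section 9.1 gives 11 per arm, response of 10% against 70%, and Fisher's exact test; Section 9.2 gives two-sided 0.05. Exact power is the sum over all pairs (a, b) of Bin(a; 11, 0.10) × Bin(b; 11, 0.70), counted where the Fisher p-value is at most 0.05. The result is 0.755 (stated: 76%). The achieved size at 10% in both arms is 0.0017 (stated: 0.002). Both reproduce. The timing point does not alter them; they serve as a yardstick in step 5.

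**2. Calendar, counting Week 12 as day 84.**

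| Item | Arithmetic | Days |
|---|---|---|
| Week 12 visit | 84 ± 3 | 81 to 87 |
| Colonoscopy, Section 7.4 | 81 − 7 to 87 + 7 | 74 to 94 |
| Colonoscopy, Table 1 | 84 ± 3 | 81 to 87 |
| Planned end of blinded supply | 6 supplies × 14 days | 84 |

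The early side raises no difficulty. The longest drug-free gap is 84 + 7 − 84 = 7 days for a visit on day 84, and 87 + 7 − 84 = 10 days for a visit at +3. Both assume no leftover capsules.

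**3. Drug remaining.** The half-life is 26 to 31 hours (Section 2.2.2, Elimination). With first-order elimination, the fraction left is 0.5^(hours ÷ half-life).

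| Gap | Half-life 31 h | Half-life 26 h |
|---|---|---|
| 7 days (168 h) | 5.42 half-lives, 2.3% left | 6.46 half-lives, 1.1% left |
| 10 days (240 h) | 7.74 half-lives, 0.5% left | 9.23 half-lives, 0.2% left |

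**4. The rules for a colonoscopy k days after the visit, k from 1 to 7.**

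- The Section 7.4 window permits it.
- The order in Sections 5.7 and 7.4 puts unblinding at k days after the visit or later.
- The entry criteria in Section 5.7 put open-label eligibility at k days after the visit or later.
- Section 7.4 puts open-label dispensing at the visit, that is, at day 0 of this count.

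The last line cannot hold with the other three when k is 1 or more. For k of 0 or less there is no conflict.

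**5. What dilution would cost, as an assumption only.** The documents give no effect of a late colonoscopy on response. With 11 per arm and placebo at 10%, exact power by active-arm response is:

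| Active response | 70% | 65% | 60% | 50% |
|---|---|---|---|---|
| Power | 0.755 | 0.66 | 0.56 | 0.36 |

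Ten percentage points is about one responder in the active arm (0.10 × 11 = 1.1).

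**The case against.** The strongest reply is that the intended order is clear. Sections 5.7 and 7.4 both put the colonoscopy before unblinding, and the synopsis has the same general sequence. This stands, and it limits the point.

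A reader might infer from the 7-day allowance that SES-CD and washings can be taken after unblinding, or while a placebo subject is already on open-label posaconazole. Such a reader might add the Absorption statement that "Steady-state plasma concentrations are attained by Day 6 at the 300 mg dose" and conclude that a control subject could be at steady state when scored. The documents do not support this. Unblinding follows the colonoscopy in both sections, and open-label entry needs the SES-CD that the colonoscopy provides. Endoscopy on crossover drug would breach both sections; the window does not permit it.

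Three further replies have weight:

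- **Central reading.** The synopsis has the primary SES-CD read centrally, which reduces the influence of a local endoscopist who knows the arm. However, no section says that the central reader is blinded or finishes before unblinding, and central reading does nothing about washout.
- **Undocumented effect.** The half-life describes systemic elimination. The documents give no rate for mucosal fungal regrowth or for change in SES-CD over 7 to 10 days.
- **Direction.** Loss of effect off drug would most plausibly pull the contrast towards no difference. That is less serious than a broken blind. The 7- and 10-day gaps are also extremes of the windows, not typical cases.

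None of these removes the contradiction between the late side of the window and dispensing at the visit, or the absence of blinded supply to cover the gap.

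**Conclusion.** The concern holds as an internal contradiction with a possible off-drug endpoint. For a colonoscopy 1 to 7 days after the Week 12 visit, the window, the order of unblinding, the open-label entry criteria and dispensing at the visit cannot all be met, and no section resolves this. A site that does nothing wrong can measure SES-CD and washings up to 7 days after planned supply ends, or up to 10 if the visit is at +3, with about 2% of drug or less remaining. This rests on first-order elimination at the stated half-life, supply ending on day 84 and no leftover capsules.

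Any resulting bias falls on the active arm and would probably dilute the contrast. Its size is unknown, and the power figures below 70% response are illustrations. Early unblinding is a risk only where a site departs from Sections 5.7 and 7.4. The case for changing the plan rests on the primary endpoint depending on this one procedure in 24 subjects, and on the low cost of the remedy.

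**What to change.** In Section 7.4:

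1. Change the Week 12 colonoscopy window from plus or minus 7 days to −7 to 0 days relative to the Week 12 visit, and no later than the end of the blinded supply. The second condition is needed because a visit at +3 days would otherwise still allow a colonoscopy on days 85 to 87.
2. State that the colonoscopy, biopsies, washings and recorded local SES-CD must be complete before the code is broken.
3. Reconcile the timing of unblinding and dispensing across Sections 5.7, 6.7.3 and 7.4 and Table 1, including the differing colonoscopy windows. How dispensing is arranged is for the sponsor to settle; the need is for one consistent statement.

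The new window should apply to the scheduled Week 12 visit. Section 7.4 also covers early termination, which cannot be foreseen, and Table 1 footnote 1 already gives its own timing for that case.

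The cost is a short amendment and slightly tighter endoscopy scheduling. No procedure is added, and the earliest permitted day (74) is already allowed.

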#### **7.5 Weeks 16, 20, 24, 28, 32 ( $\pm 3$ days)**

This visit may be conducted within three days of the specific time-point marking the number of weeks since baseline visit. The following tasks will be conducted at these visits:

- Assessment of concomitant medications.
- Targeted physical examination, vital signs, and weight.
- Laboratory studies: serum chemistries, complete blood count with automatic differential, lipid panel, and stool calprotectin and microbiome (not collected at W28 & 32), blood for transcriptomics
- Review of bowel movement diary.
- Calculation of CDAI and PRO2 scores
- IBDQ and SF36 assessments
- Adverse event monitoring.

- Weeks 16, 20, and 24: Female subjects receiving open label posaconazole will undergo urine pregnancy test, and all subjects receiving open label posaconazole will undergo EKG.

## **7.6 Week 36 visit (or final follow up visit after early termination)**

The following tasks will be conducted at this visit:

- Assessment of concomitant medications.
- Complete physical examination, vital signs, and weight.
- Laboratory studies: urine pregnancy test in women of childbearing potential, hsCRP, serum chemistries, complete blood count with automatic differential, lipid panel, and stool calprotectin.
- Calculation of CDAI and PRO2 scores
- Eligibility assessment based on collected data.
- Adverse event monitoring.
- Review of bowel movement diary.
- IBDQ and SF-36 assessments.
- Colonoscopy with biopsies (RNALater & Formalin) and washings scheduled  $\pm 7$  days of this visit for calculation of SES-CD. Biopsies & washings should be obtained from same area of each region as screening samples.

## **8 Assessments**

### **8.1 Efficacy measures**

#### **8.1.1 Bowel movement diary**

Subjects will be provided with a daily diary to record bowel movement frequency and abdominal pain. Subjects will record the usual number of stools per day when not having a flare. Within their daily bowel movement history, subjects will record the number of bowel movements per day, and presence of blood in stool.

#### **8.1.2 Crohn's disease activity Index (CDAI), PRO2 and Simple Endoscopic Score for Crohn's disease (SES-CD)**

These scoring systems assess Crohn's disease activity. The CDAI score ranges from 0 to 600, and has traditionally been used to assess clinical disease activity for Crohn's disease clinical trials. Clinical remission will be defined by a CDAI score of  $<150$  points AND a patient-reported outcome 2-item (PRO2) score of abdominal pain score  $\leq 1$  AND stool frequency  $\leq 3$ . (See Appendix for calculations of both CDAI and PRO2). The SES-CD will determine endoscopic activity for eligibility as well as for determining mucosal improvement (See Appendix for SES-CD calculation).

#### **8.1.3 Health-related quality of life**

The following quality-of-life measures are recorded by subjects at the corresponding visits (pending permissions):

- Inflammatory bowel disease questionnaire (IBDQ)
- Short Form SF-36 (SF-36)

### **8.2 Laboratory markers**

- Serum chemistry (sodium, potassium, chloride, magnesium, phosphorous, bicarbonate, blood urea nitrogen, creatinine, glucose, total protein, albumin, alanine aminotransferase, aspartate

CONFIDENTIAL

This material is the property of Cedars-Sinai Medical Center.

aminotransferase, total bilirubin, direct bilirubin, alkaline phosphatase, gamma-glutamine transferase,)

- Complete blood count with automated differential (hemoglobin, hematocrit, white blood cell count, platelet count)
- Urinalysis (pH, color, blood, specific gravity, glucose, protein, leukocyte esterase, nitrite) with microscopy if presence of blood, leukocyte esterase, nitrite, or if there is a clinical indication
- Serum  $\beta$ -hCG
- Urine  $\beta$ -hCG
- High-sensitivity C-reactive protein (hsCRP)
- Lipids
- Stool tests for C difficile, enteric pathogens, calprotectin

### **8.3 Pharmacokinetics laboratory markers**

- Serum posaconazole will be assessed at weeks 2, 4, 6, 8, 10, and 12. The exact time of day and date of collection will be recorded.

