## Elimination

Following administration of Noxafil oral suspension, posaconazole is predominantly eliminated in the feces (71% of the radiolabeled dose up to 120 hours) with the major component eliminated as parent drug (66% of the radiolabeled dose). Renal clearance is a minor elimination pathway, with 13% of the radiolabeled dose excreted in urine up to 120 hours (<0.2% of the radiolabeled dose is parent drug). Posaconazole delayed-release tablet is eliminated with a mean half-life (t1/2) ranging between 26 to 31 hours.

CONFIDENTIAL

This material is the property of Cedars-Sinai Medical Center.

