## **4.6 Pharmacokinetics Endpoints**

- Serum posaconazole concentrations at weeks 2, 4, 6, 8, 10, and 12. Relationship between posaconazole serum concentration and clinical and antifungal effects

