#### **6.7.3 Dispensing of Study Drug**

Patients will be dispensed a 2-week supply of study drug (or placebo) at each of the following study visits: baseline (week 0), and weeks 2, 4, 6, 8, and 10. Study drug reconciliation will be performed to document drug assigned, drug consumed, and drug remaining. This reconciliation will be logged on the drug reconciliation form and signed and dated by the study team.

Patients who are eligible to receive open label posaconazole will be dispensed a 4-week supply of study drug at weeks 12, 16, and 20.

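### Posaconazole samples carry a clock time but no last-dose time, and a 2-week supply with visits up to 3 days late can put an adherent subject's sample about 96 h after the last dose

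*Combined protocol and SAP*

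**What the plan says.** All references are to the combined protocol and SAP.

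- **Sampling.** Section 8.3: "Serum posaconazole will be assessed at weeks 2, 4, 6, 8, 10, and 12", and then "The exact time of day and date of collection will be recorded". That is the whole collection specification.
- **Use of the levels.** Section 4.6 lists as an endpoint the "Relationship between posaconazole serum concentration and clinical and antifungal effects", and the synopsis does the same. Section 9.2 gives this endpoint no method; its pharmacokinetic line names nicotine instead of posaconazole.
- **Supply.** Section 6.7.3: "Patients will be dispensed a 2-week supply of study drug (or placebo) at each of the following study visits", namely weeks 0, 2, 4, 6, 8 and 10. No overage is stated.
- **Windows.** Section 7.3: "These visits may be conducted within three days of the specific time-point marking the number of weeks since baseline visit". Section 7.4 says the same of week 12: "This visit may be conducted within three days of the specific time-point marking the number of weeks since baseline visit". Both windows are anchored to baseline, not to the preceding visit.
- **Dose records.** Section 6.4 judges compliance by counting leftover units. Section 6.7.3 reconciles how much was handed out, used and left. The diary in section 8.1.1 covers bowel symptoms and pain, not dosing. Only the first dose is observed (section 6.3).

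**The concern.** A serum level can be interpreted only against the time since the last dose. Clock time alone does not give that, because doses are self-administered at home. If the only gap in knowledge were the hour within a normal day of dosing, the error would be small. But the supply covers 14 days, the next visit may come on day 17, and the sample is drawn at that visit. A subject who follows every instruction can then show a low level that reflects the calendar and not the individual's exposure.

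At stake is the concentration-effect endpoint. It rests on about 12 subjects (24 randomised 1:1), and Table 1 schedules no pharmacokinetic draws after week 12, so open-label subjects add no data. Endoscopic response, clinical remission and *Malassezia* reduction are all assessed at week 12, which makes the week-12 level a natural one to pair with outcome.

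**Working it through.** **Inputs**

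- Half-life of the delayed-release tablet: "ranging between 26 to 31 hours" (section 2.2.2, Elimination).
- Steady state: "Steady-state plasma concentrations are attained by Day 6 at the 300 mg dose" (section 2.2.2, Absorption). Every planned sample is therefore at steady state if dosing is uninterrupted.
- Cmax and Cmin from the steady-state table in section 2.2.2: 2764 and 1785 ng/mL in healthy volunteers, 2090 and 1310 ng/mL in patients; median Tmax 4 h.
- Supply 14 days; visits within 3 days of nominal.

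**Reproducing the protocol's own figures**

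- Cav = AUC/24: 51618/24 = 2150.75 (stated 2151); 37900/24 = 1579.2 (stated 1580).
- Half-life implied by a log-linear fall from Cmax at 4 h to Cmin at 24 h, 20 × ln 2 / ln(Cmax/Cmin): 31.7 h in healthy volunteers (stated 31) and 29.7 h in patients (inside the stated range).

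The figures agree well enough to use simple exponential decline.

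**Timing within a normal dosing interval**

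Cmax/Cmin = 2764/1785 = 1.55 and 2090/1310 = 1.60.

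**Timing after the supply ends**

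The first dose is on day 0, so 14 days of drug end on day 13. A sample on day 14 is about 24 h after the last dose, the usual trough. A sample on day 17 is about 96 h after it. With d daily doses missed, the fraction of the 24 h trough is 2^(−24d / half-life):

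| Doses missed | Hours since last dose | Half-life 26 h | Half-life 31 h |
|---|---|---|---|
| 1 | 48 | 0.527 | 0.585 |
| 2 | 72 | 0.278 | 0.342 |
| 3 | 96 | 0.147 | 0.200 |

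Three missed doses take the patient trough of 1310 ng/mL to 192–262 ng/mL, a 5- to 7-fold fall (1/0.200 = 5.0; 1/0.147 = 6.8).

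**How many days can be missed**

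If leftovers are kept, 14k days of drug have been handed out before the k-th follow-up visit, which falls on day 14k + 3 at the latest. Missed days therefore total at most 3 per subject over all six visits. Enumerating all 7^6 whole-day visit patterns confirms this. If leftovers are taken back at each visit, one visit 3 days early and the next 3 days late gives a 20-day interval and 6 missed days.

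**Effect on ranking subjects by exposure**

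This is a simulation. Its assumptions are between-subject CV 42–50% (the patient Cav and Cmin CVs), half-life 26–31 h, visit delay uniform over −3 to +3 days, otherwise full adherence, and samples without a run-out taken 4–24 h after dosing. The entries are correlations with the subject's true exposure level.

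| | Samples after a run-out | One sample, average over visits | Week-12 sample | Mean of six |
|---|---|---|---|---|
| No run-out | 0% | 0.93–0.96 | 0.93–0.96 | about 0.99 |
| Leftovers kept | 23% | 0.57–0.69 | 0.71–0.81 | 0.96–0.98 |
| Leftovers taken back | 43% | 0.34–0.46 | 0.33–0.43 | 0.83–0.90 |

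**The case against.** The strongest reply is that the harm is bounded. Not knowing the hour within a dosing interval costs little: one sample still correlates 0.93–0.96 with true exposure. Six samples are taken, and their mean holds up well if leftovers are kept. The plan specifies no single-visit analysis. This is neither the primary nor a key secondary endpoint, and the trial is a pilot. A case report form outside the document may already capture the last dose. All of this stands and limits the weight of the point. It does not remove it, because the plan does not commit to a six-sample mean either.

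Four stronger readings are tempting, and the document does not support them.

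- **That a run-out cannot be told from low exposure.** Reconciliation under section 6.7.3, set against the recorded sample date, would show nothing left and more days elapsed than supplied. That flags a shortfall. It does not date the last dose: the missed days could have come earlier in the interval.
- **That gaps of 6 days are built in.** They need leftovers to be taken back at routine visits. Section 6.4 has subjects bring their containers, and section 5.6.1 requires return of drug on withdrawal; neither says what happens to leftovers at an ordinary visit.
- **That supply gaps trip the compliance rule in section 6.4.** A subject who has run out has no unused units to count. Even measured against elapsed days, 14/17 = 82% is above the 80% limit. A breach needs at least 18 days (14/18 = 78%), and two in a row need 36, while two consecutive intervals span at most 28 + 6 = 34. The two-visit withdrawal rule cannot be reached by supply alone.
- **That the level is 15–20% of trough three days after the last dose.** At 72 h it is 28–34%; the 15–20% figure belongs to about 96 h.

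**Conclusion.** The point holds as a modest, cheap improvement. As written, the plan lets an adherent subject be sampled about 96 h after the last dose at 15–20% of the usual trough, and does not collect the one item that would identify the sample for what it is. Analyses that pair a single visit's level with outcome are materially exposed. A six-sample mean is little affected if leftovers are kept and noticeably affected if they are taken back.

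This rests on three assumptions: exponential decline at the stated half-life; a 2-week supply that covers exactly 14 dosing days including the loading day (the capsule count is not given); and, for the correlations only, the simulation assumptions above. The primary endpoint is untouched.

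**What to change.** 1. Record the date and time of the last dose at every pharmacokinetic draw (section 8.3).
2. In section 9.2, state that the exposure-response analysis uses time since last dose. Flag samples taken more than one dosing interval after the last dose, and add a sensitivity analysis that excludes them. Correct the substance named there at the same time.
3. Reconcile the 2-week supply in section 6.7.3 with the ±3-day windows in sections 7.3 and 7.4, and state what happens to leftover capsules at routine visits. How this is resolved is for the sponsor.

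The cost is one or two case-report-form fields, a few sentences of plan text and a small amount of analysis work. Last-dose times not asked for at the draw cannot be reliably recovered later, so the fields need to be in place before sampling.
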